Vitamin D₃ also known as cholecalciferol, has been selected as the treatment since it is the natural form of vitamin D, the more widely used supplement, and now recommended for clinical practice (34). The Institute of Medicine recommends 600 IUs of Vitamin D per day for individuals up to age 70 (101). Thus, the 5000 IUs dose will approximate follow that recommendation (600 IUs x 7 days= 4200 IUs) and be given once per week as well. The use of a dose with the minimum recommended amount for comparison is consistent with other studies examining the benefit of vitamin D supplementation on health outcomes (35, 95). Bio Tech Pharmacal, Inc. will prepare the vitamin D₃ supplements. This company complies with all applicable Food and Drug Administration regulations and follows Good Manufacturing Practices that are designed to ensure that the products meet the highest quality standards.

b. Treatment Randomization. A stratified block randomization will be used with blocks of random size 2, 4 and 6. There will be two strata based upon depression symptom severity using the CES-D guidelines (118). These strata will be (1) moderate severity for CES-D scores of 16 to 26 and (2) high severity for CES-D scores greater than 26. In our previous work, about half of the women were in each stratum at baseline. With stratified randomization, factors associated with depression should be more evenly distributed as randomization with stratification induces more balanced groups (119). A randomization list will be developed by [name], statistician and co-investigator. The list will be retained by the research pharmacist at Loyola, who is independent from those involved with the conduct of the study. The research pharmacist will use the list to assign subjects to the treatments..

c. Blinding. The study supplements will be administered by the pharmacist in a blinded fashion during the study so that the patient and clinical site personnel (except for the pharmacist) will not be aware of the patient's assigned treatment.

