Hypothesis 1: Women receiving 50,000 IUs vitamin D supplementation will report fewer depressive symptoms (primary outcome), increased diabetes self-management mediated by depression improvement (secondary outcome), and have a lower systolic BP (exploratory) compared to those 5000 IUs at three and six months follow-up.

For analysis of the primary outcome (depressive symptoms) generalized, linear, mixed models (GLMM) for repeated measures will be used (154). The proposed model will have one between-subjects variable GROUP (vitamin D supplementation; control) with two levels and one within-subjects variable TIME with three levels (baseline, 3 and 6 months). The test of the hypotheses will hinge on the GROUP by TIME interaction as an indication of group differences in the variable of interest over time. A given hypothesis will be supported with the finding of a statistically significant GROUP by TIME interaction, and the finding that the means are in the hypothesized direction. GLMM will be implemented using SPSS which will provide estimates of the means for each outcome variable by time and treatment groups. The results will be summarized with adjusted means and 95% confidence intervals. A compound symmetric covariance structure will be assumed. If necessary, other covariance structures, such as Huynh-Feldt, will be investigated. An intention-to-treat analysis (ITT) which includes an analysis of completers and noncompleters will also be done using GLMM. Stratification by depression severity should provide comparable groups at baseline; however, differences will be assessed. All analyses will control for baseline values of body composition (body fat), race (white compared with nonwhite), and time at entry into the study (as season of the year, winter, summer, spring, fall) as previously done by our consultant, [name], in his vitamin D trials. Other covariates, related to diabetes (length of time with diabetes, HBA1c), lifestyle factors, (physical activity, diet), and previous depression will be added to generate a multivariate model which is parsimonious and based on the clinical relevance and statistical significance of these factors.

For analysis of the secondary outcome (self-management), regression analysis will be used to test whether an improvement in self-management is mediated by an improvement in depressive symptoms (Figure). The Preacher and Hayes macro add-on for SPSS will be used. This technique estimates the path coefficients and

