d. Sample Size Estimation. Based on our power estimates, a sample of 75 women per group will be needed for a final sample of 150 women. We have planned for a conservative attrition (15%) which is higher than our Sunshine pilot (8%) but consistent with our SWEEP trial (59). **Therefore, 180 (90 per group) will be enrolled into the treatment arms.** Thus far, out of 169 patients enrolled, only 83 (49%) have been randomized to treatment arms. Thus, we will enroll 360 as we have had a screen failure of almost 50% to allow for a sufficient number of persons to be randomized. For the power analysis, we used a repeated measures approach formulae developed by Hedeker et al. (158) which allows comparisons of the group means across time while adjusting for baseline values and accounting for the correlation between baseline and follow-up observations. We have assumed a 2 tailed test with a type I error rate of 0.05 for each outcome. **Depression:** There was a 14 point decrease in depression from baseline to 6 months following vitamin D supplementation using the CES-D (see pilot data). Using the control group in the SWEEP study (which had the same enrollment criteria for depression and did not receive treatment), there was a 7 point decrease in depression (28.8 to 21.4) as depression symptoms can improve without treatment. Given these group difference, the effect size is .46. A sample size of 30 per group would provide 95% power. We also powered for depression remission (CED-D < 16) as other depression trials (159). In our vitamin D study, 55% of women had remission of their depression at 3 months and 63% at 6 months. Using the control group data from the SWEEP study, 30% had remission of depression at 3 months and 20% at 6 months. Having this information, a sample size of 75 per group (n=150) would be needed to detect differences in depression remission at 3 months and a sample of 25 per group (n=50) to see the difference at 6 months. **Diabetes Self-Management:** There were significant differences from baseline to six months (see pilot data) to calculate the effect sizes. We calculated an effect size of .70 for diabetes distress and .33 for self-care. For diabetes self-efficacy, an effect size of .30 based on our previous research (SWEEP) will be used. A sample of 75 per group (n=150) will achieve 85% power on these study outcomes. **Blood Pressure:** We observed a decrease of 8 mmHg in the vitamin D study but no change in a control group from the SWEEP study (136.2 mmHg to 135.9 mmHg). Pfeifer et al. (96) reported a 7% decrease in blood pressure in women after 800 IUs of D₃ for 6 weeks. To be conservative, we will assume a difference of about 5 mmHg to account for the placebo effect and regression to the mean phenomena commonly observed in clinical trials. This difference yields an effect size of about 0.3. A final sample of 150 (75 per group) would provide 80% power to assess this outcome. **Inflammation (Exploratory):** Using pilot data of [name] (see pilot data) a sample size of 75 per group provides 85% power to detect differences between groups on depression and inflammation. **For the meditational analyses,** power was estimated using effect sizes from our previous research and current pilot study. Although the depression effect sizes discussed above are large (160), a more conservative approach anticipating medium effect sizes was employed for the mediation analysis. With medium effects for self-care outcomes, a total sample of 135 would achieve 95% power.

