
Sample size estimation:

For the sub-study (FAMDD), the qualitative component of the study, the sample size proposed was 50 women. For the quantitative component, it is estimated that since these tools have been used previously, that the estimate needed for adequate power will be determined by power analysis. An a-priori sample size by these investigators for multiple regression indicates with a medium effect size, $p = .05$, power of .80 and up to 6 independent variables a minimum sample of 97 will be needed for quantitative analysis.

6. Potential Problems and Alternative Solutions. Although subject accrual is a concern for all research, we have been successful in our previous studies. We have established relationships with key clinical sites (see diabetes educators, physicians support letters) which have reported a high volume of accessible patients (see

2b, recruitment table). Although attrition is another potential issue, it has been low in our previous studies (6% pilot vitamin D, 15% SWEEP). And, we have provided steps for addressing adherence, retention, and drop-outs (see 3d). To prevent measurement issues, protocols for training of staff to ensure consistency with the collection of data have been established in our prior work. It is possible that factors like diet and sunshine may impact on vitamin D levels. Although the impact of these variables in our pilot work was not substantial, they will be measured. Because body fat may affect vitamin D levels, body composition has been added as measurement. Treatments will be assessed at all time points and evaluated for their contribution to the study outcomes. In our prior work, we did not see significant changes in medications as women were on established medications prior to enrollment. The placebo effect may have been a factor for the positive findings in our one-arm pilot study; hence a randomized trial is the next logical step. Study staff will be blinded to the treatment and we have protocols if the blind needs to be broken (see 1c-e). Staff will not provide additional support to the patient for treatment; however, protocols for increased depression have been delineated (3b). Finally, it is possible that if depression improves, self-management may not. Therefore, the next planned study would be a randomized trial to see if treating depression with vitamin D prior to diabetes self-management education could enhance learning and self-management outcomes.

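### The primary CES-D test is valid but uses baseline CES-D only as change from baseline; adjusting for that score would add power if the true effect is smaller than planned

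*Combined protocol and SAP*

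**What the plan says.** Section V.5.b (Data Analysis, Hypothesis 1) specifies a repeated-measures mixed model with GROUP (two levels) and TIME (baseline, 3 and 6 months), with compound symmetry as the starting covariance. On the decision rule it says: "The test of the hypotheses will hinge on the GROUP by TIME interaction". Support also requires the means to lie in the hypothesised direction.

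On covariates, the same section says: "All analyses will control for baseline values of body composition (body fat), race (white compared with nonwhite), and time at entry into the study". Diabetes duration, HbA1c, activity, diet and previous depression are candidates for a further model. Baseline CES-D and the CES-D randomisation stratum (V.1.b) are in neither list, and the arms are not constrained to share a baseline mean.

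Section V.5.d describes the power method as one that "allows comparisons of the group means across time while adjusting for baseline values and accounting for the correlation between baseline and follow-up observations". The planned difference there is 7 points: a 14-point fall in the one-arm pilot less a 7-point fall in the control group of an earlier trial.

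**The concern.** When baseline is a level of the outcome and each arm has its own baseline mean, the GROUP by TIME interaction is a comparison of changes from baseline. A change score subtracts the whole baseline value, whatever its correlation with follow-up. Unless that correlation is high, this carries baseline noise into the comparison. Adjusting for baseline removes only the predictable part, so it is more precise in a randomised trial.

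The baseline wording in V.5.d could mean change from baseline or covariate adjustment. If it means the latter, the model in V.5.b does not carry it over.

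The loss matters only if the true effect falls short of 7 points, and the documents make that plausible. Section V.6 concedes of the pilot: "The placebo effect may have been a factor for the positive findings in our one-arm pilot study". The 7-point control fall comes from women who received no treatment, whereas the comparator here takes 5000 IU weekly.

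**Working it through.** **The plan's own figures.** The stated effect size of 0.46 for CES-D matches 7 / 7.6 / 2 = 0.46, that is, a standardised difference of 7 / 7.6 = 0.92 halved. This reading is inferred; V.5.d does not state it. A two-sample calculation at 0.92 with 30 per group gives 94.6% power, against 95% stated. The 75 per group comes from 3-month remission (55% against 30%), for which it gives 88% power. The baseline question therefore does not affect the sample size.

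**Inputs.**
- 75 per group, two-sided 0.05 (V.5.d).
- SDs 7.6, 8.9 and 8.3 at baseline, 3 and 6 months (pilot table, section IV).
- Correlation between visits: not in the documents. A common value of 0.3, 0.5 or 0.7 is assumed.
- Smaller 6-month effect: 0.4 × 8.3 ≈ 3.3 points, an assumption.
- Profile over time, also assumed: the same effect at both visits, or half the 6-month effect at 3 months. A third profile takes the 3-month effect as 0.58 of the 6-month effect, from remission differences in V.5.d: pilot "55% of women had remission of their depression at 3 months and 63% at 6 months", control "30% had remission of depression at 3 months and 20% at 6 months", giving (55 − 30)/(63 − 20) = 25/43.

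**Formula.** Both tests have 2 numerator df and are referred to F with 2 and 4n − 4 = 296 df (critical value 3.03). The noncentrality is λ = (n/2) δ′V⁻¹δ. For the planned test, V is the covariance of the two changes from baseline. For the adjusted test, V is the covariance of the two follow-up scores conditional on baseline. The other covariates are left out of both.

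**Worked case: correlation 0.5, constant 3.3 points.**
- Planned: V has variances 69.33 and 63.57 and covariance 29.33. λ = 37.5 × 3.3² × (69.33 + 63.57 − 2 × 29.33)/(69.33 × 63.57 − 29.33²) = 8.55. Power is 74%.
- Adjusted: V has variances 59.41 and 51.67 and covariance 18.47. λ = 37.5 × 3.3² × (59.41 + 51.67 − 2 × 18.47)/(59.41 × 51.67 − 18.47²) = 11.10. Power is 85%.
- For the planned test to match the adjusted test at 75 per group: 75 × 11.10/8.55 ≈ 97 per group.

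**All settings at 3.3 points (correlation 0.3 / 0.5 / 0.7).**

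| 3-month effect | Planned power, % | Adjusted power, % |
|---|---|---|
| Same as 6 months | 59 / 74 / 93 | 81 / 85 / 95 |
| 0.58 of 6 months | 47 / 62 / 84 | 66 / 73 / 88 |
| Half of 6 months | 47 / 61 / 84 | 64 / 72 / 87 |

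| Quantity | Constant effect | Half at 3 months |
|---|---|---|
| Smallest 6-month difference with 80% power, planned | 4.2 / 3.5 / 2.8 | 4.8 / 4.1 / 3.2 |
| Same, adjusted | 3.3 / 3.1 / 2.6 | 3.9 / 3.6 / 3.0 |
| Per-group n for the planned test to match the adjusted test at 75 | 121 / 97 / 82 | 112 / 94 / 82 |

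At 7 points both tests have at least 98.7% power in every one of these settings.

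**Simulation check.** Skewed baseline scores starting at 16 (mean 26.83, SD 7.6), strata split at 26, random blocks of 2, 4 and 6, and the planned model fitted with compound symmetry; 5,000 null and 3,000 effect trials per correlation.

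| Quantity, % | Planned | Adjusted |
|---|---|---|
| Type I error | 3.5 / 3.7 / 4.6 | 4.9 / 4.2 / 4.9 |
| Power, constant effect | 56 / 74 / 93 | 80 / 85 / 95 |
| Power, half at 3 months | 43 / 60 / 83 | 65 / 71 / 87 |

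The planned test holds its level and is slightly conservative. Adding the stratum once baseline is in the model changes power by no more than a point.

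**The case against.** The strongest reply is that nothing here is an error. A GROUP by TIME test with baseline as a time level is a standard, coherent analysis of change. The loss needs both an effect well under the planned one and a modest correlation. At 5 points the planned test already has 93%, 98% and nearly 100% power (constant effect), or 83%, 94% and 99.6% (half at 3 months), at correlations 0.3, 0.5 and 0.7. At 6 points it has at least 94% throughout. At a correlation of 0.8 the gain at 3.3 points is under one point. All of this stands, and it is why the point is minor.

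The 0.58 profile is a loose proxy, because remission differences do not translate into ratios of mean scores. That stands too, but the conclusion does not rest on it. The pilot means (26.83, 15.13, 12.15) show about 80% of the fall by 3 months, although within one arm. A 0.8 profile gives 52/67/88% against 73/79/91%.

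The simulated baseline starts at 16, while the entry criteria (V.2.a) also admit women on antidepressants scoring 12 or more, and women who qualify on the average of two screens. A different baseline spread would change the size of the gain, but the direction would stay the same at the correlations examined.

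Finally, the sponsor may already intend adjustment, given the V.5.d wording. If so, V.5.b needs to say it; as written, it does not.

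**Conclusion.** The point holds as a minor one. Baseline CES-D enters the primary test only through change from baseline. The test controls type I error, the sample size does not rest on it, and at 7 points there is nothing material to gain.

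If the true 6-month effect is nearer 3.3 points, baseline adjustment raises power by about 18 to 22 points at a correlation of 0.3, 10 to 11 at 0.5, and 2 to 3 at 0.7, across the three tabulated profiles. These sizes rest on the assumed correlations, the assumed effect and its profile, and the pilot SDs carrying over to this trial.

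**What to change.** Amend V.5.b before unblinding in one of two ways:
- Model the 3- and 6-month CES-D scores with baseline CES-D as a covariate, and test the treatment effect jointly at both visits (2 df).
- Keep all three time points, but constrain the arms to a common baseline mean and test the group differences at the two follow-up visits jointly.

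Adding baseline CES-D as a covariate while baseline also stays an unconstrained TIME level would not deliver the gain. Keep the requirement that the means lie in the hypothesised direction.

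Include the CES-D stratum as assigned at randomisation, to reflect the design; it is not a source of power. An unstructured covariance is optional and bears only on the single-visit intervals. State in V.5.d which form of baseline adjustment the power method assumes, so that the two sections agree.

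The cost is wording only, since baseline CES-D and the stratum are already recorded for every randomised woman. Fixing it in advance matters because V.5.b chooses further covariates partly on statistical significance, so a later decision to adjust could look data-driven.

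### Compound symmetry, and the Huynh-Feldt fallback, give every within-woman change in CES-D the same variance, so intervals for change contrasts may be mis-sized in a direction the documents cannot settle

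*Combined protocol and SAP*

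**What the plan says.** Section V.5.b (Data Analysis, Hypothesis 1) sets up a repeated-measures mixed model with a two-level group factor and "one within-subjects variable TIME with three levels (baseline, 3 and 6 months"). Baseline is therefore an outcome level. On inference it says: "The test of the hypotheses will hinge on the GROUP by TIME interaction". On reporting it says: "The results will be summarized with adjusted means and 95% confidence intervals". The hypothesis itself is framed at both the 3- and the 6-month follow-up.

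The covariance statement is "A compound symmetric covariance structure will be assumed. If necessary, other covariance structures, such as Huynh-Feldt, will be investigated". Huynh-Feldt is offered as an example, so the list is open. An unstructured matrix is not named, and nothing says what would make a change of structure necessary.

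The same procedures are reused for blood pressure and, under Hypothesis 2, for the inflammatory markers.

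The pilot table in section IV gives CES-D SDs of 7.6, 8.9 and 8.3 at baseline, 3 and 6 months. Section V.5.d (Sample Size Estimation) refers to "accounting for the correlation between baseline and follow-up observations" but gives no value, and no SD of change appears anywhere.

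**The concern.** The interaction is built from within-woman changes: 0-3, 0-6 and, by implication, 3-6 months. A two-degree-of-freedom test does not say when the arms differ. Because the hypothesis names both follow-up visits, readers will look to contrasts at each visit. The standard error of such a contrast depends on the variance of that particular change.

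Compound symmetry gives all three changes one variance. So does Huynh-Feldt, which frees the visit variances but not the variances of change. If the true variances of change differ, moving from the default to the named fallback leaves the contrast intervals where they were. With no rule for switching, the covariance structure of the primary model could also be chosen after the data have been seen.

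**Working it through.** The plan gives no figure for the covariance of CES-D changes, so there is nothing of its own to reproduce. The inputs are the three pilot SDs (section IV table), two-sided alpha of 0.05 and 75 women per arm (section V.5.d). **All correlations below are assumptions.** The arms are taken to share one covariance matrix and the data to be complete.

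**Step 1: what each structure implies.**
- Compound symmetry: Var(Yi - Yj) = 2σ²(1 - ρ) for every pair of visits.
- Huynh-Feldt: Cov(Yi, Yj) = (σi² + σj²)/2 - λ. Then Var(Yi - Yj) = σi² + σj² - 2Cov(Yi, Yj) = 2λ for every pair of visits.

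Fitted numerically to the same true matrices, the two structures gave the same common value and the same standard-error ratios in every setting tried.

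**Step 2: visit means, with no correlation needed.** The mean variance is (57.76 + 79.21 + 68.89)/3 = 68.62, a common SD of 8.28. Compound symmetry then makes the interval 9% too wide at baseline (8.28/7.6 = 1.09) and 7% too narrow at 3 months (8.28/8.9 = 0.93, coverage about 93.2%). At 6 months it is about right (8.28/8.3 = 1.00). Huynh-Feldt lets each visit have its own variance and removes this error.

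**Step 3: change contrasts.** The true variance is Vij = si² + sj² - 2·rij·si·sj. The model value V is the mean of the three Vij. The ratio of model SE to true SE is √(V/Vij); the arm sizes cancel. Type I error is 2[1 - Φ(1.96 × ratio)].

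Example, correlations .4/.35/.65 (0-3, 0-6, 3-6 months):
- V for 0-3 = 57.76 + 79.21 - 2(.4)(7.6)(8.9) = 82.9
- V for 0-6 = 57.76 + 68.89 - 2(.35)(7.6)(8.3) = 82.5
- V for 3-6 = 79.21 + 68.89 - 2(.65)(8.9)(8.3) = 52.1
- Mean = 72.5; ratio for 0-6 = √(72.5/82.5) = 0.937; type I error 6.6%

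| Assumed r (0-3 / 0-6 / 3-6) | True variances | Common value | SE ratios | Type I error, 0-6 |
|---|---|---|---|---|
| .5 / .5 / .5 | 69.3, 63.6, 74.2 | 69.0 | 0.998, 1.042, 0.964 | 4.1% |
| .5 / .5 / .6 | 69.3, 63.6, 59.5 | 64.1 | 0.962, 1.004, 1.038 | 4.9% |
| .5 / .4 / .6 | 69.3, 76.2, 59.5 | 68.3 | 0.993, 0.947, 1.072 | 6.3% |
| .4 / .35 / .65 | 82.9, 82.5, 52.1 | 72.5 | 0.935, 0.937, 1.180 | 6.6% |
| .3 / .2 / .7 | 96.4, 101.4, 44.7 | 80.8 | 0.916, 0.893, 1.345 | 8.0% |
| .7 / .5 / .7 | 42.3, 63.6, 44.7 | 50.2 | 1.089, 0.888, 1.060 | 8.2% |

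A ratio below 1 means an interval that is too narrow; above 1, too wide.

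**Step 4: what fixes the direction.** With the pilot SDs, both baseline changes come out too narrow only if the 3-6 month correlation exceeds about .45, .53 or .61 when the common baseline-to-follow-up correlation is .3, .4 or .5. Selecting on baseline from a population that was otherwise compound symmetric pushes the other way: ratios of about 1.01 to 1.04 for baseline changes and 0.93 to 0.99 for 3-6 months.

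**Step 5: the interaction test.** Simulated with 150 women, its type I error was about 5% to 6% across the settings.

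**The case against.** The strongest reply is that nothing has been shown to go wrong with the planned decision. The primary test is the overall interaction, and it holds its level to within about a percentage point. The intervals the plan promises accompany adjusted means, and Huynh-Feldt does repair those. The open wording already permits an unstructured matrix. The pilot SDs are weak evidence of unequal variances: with 46 completers, (8.9/7.6)² = 1.37 gives p of about .20 to .28 for paired correlations of .3 to .6. They are also raw, one-arm SDs, whereas the planned model adjusts for covariates. All of this stands, and it limits the point to the change contrasts and to the missing rule.

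A reader might infer more: that intervals for change from baseline are too narrow and those for 3 to 6 months too wide. The documents do not support that as fact. It requires the two on-treatment scores to be sufficiently more correlated with each other than with baseline, and no correlation is reported. Equal correlations of .5 reverse it, entry selection on CES-D points the other way, and at .7/.5/.7 the 0-3 month interval is 9% too wide. The plan also names no interval for the 3-to-6-month change, so the largest distortions in the table concern a contrast that is not planned.

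What the reply does not answer is that the stated default and the only named alternative share the same restriction, and that permission to look at other structures is not a pre-specified choice.

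**Conclusion.** The structural point holds without assumptions: both named structures give all within-woman changes one variance, so Huynh-Feldt cannot correct change contrasts that compound symmetry gets wrong. Those intervals may be mis-sized, and the direction depends on unreported correlations. Over the range tried with the pilot SDs, the baseline-to-6-month interval goes from 4% too wide to about 11% too narrow (type I error about 4.1% to 8%). These sizes rest on the assumed correlations, on SDs from a small one-arm pilot, on equal covariance in the two arms and on complete data. The overall interaction test is close to nominal, so this is not a threat to the primary decision. It is a worthwhile, inexpensive improvement to the error bars readers will use at each visit, and it closes a choice that is now left until after the data are seen.

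**What to change.** In section V.5.b, replace the covariance sentences with a pre-specified unstructured 3x3 matrix for the primary CES-D model, using Satterthwaite or Kenward-Roger degrees of freedom. Name a simpler structure to be used only if the unstructured model fails to converge. Apply the same rule to the blood pressure and biomarker models that reuse these procedures. Each change then keeps its own variance, and coverage is about 95% for all three contrasts whatever the correlations.

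The cost is six covariance parameters (three variances and three covariances) instead of two. With about 150 women that is negligible, and only the wording of the plan changes.
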